7.4.5.2. Withdrawal Period

Vital sign data will be summarized by presenting descriptive statistics of observed values, change from DB baseline and OL baseline, and changes from withdrawal baseline by visit and analysis group.

7.4.6. Assessments of Withdrawal Effects (CSSA, DESS, HAM-A, and MADRS)

7.4.6.1. Treatment Period

MADRS total score, HAM-A total score, and the individual scores collected in the OL treatment period will be summarized by presenting descriptive statistics (N, mean, median, and range) of observed values and change from DB baseline and OL baseline over time by analysis group for safety population.

7.4.6.2. Withdrawal Period

MADRS total score, HAM-A total score, and each of the individual item scores in the withdrawal period will be summarized by presenting descriptive statistics (N, mean, median, and range) of observed values and change from DB baseline, OL baseline, and withdrawal baseline by analysis group and visit; a similar analysis will be performed by gender as well.

CSSA total score, DESS total score, and the individual scores will be summarized by presenting descriptive statistics (N, mean, median, and range) of observed values and change from withdrawal baseline by analysis group and visits based on the withdrawal population; the visits will be displayed in an order defined as follow: withdrawal Baseline, day 1-2, day 3-4, day 5-6, day 7-8, withdrawal Week 1, day 9-10, day 11-12, day 13-14, withdrawal Week 2, day 15-16, day 17-18, day 19-20, day 21-22, withdrawal Week 3. See [Section 6.1.2.2](#) for details about how to define these analysis visits per both clinic and non-clinic visits. A similar analysis will be performed by gender as well. Number and percentage of subjects with a new symptom or worsen old symptom for each DESS individual score (ie, each individual score of DESS with value of 1) by study visit and the worst case during the withdrawal period will be summarized based on the withdrawal population as well.

The number and percentage of subjects in each of the following breakdown will be summarized by study visit during the withdrawal period.

- CSSA total score: 0-7, 8-15, 16-30, 31-45, 46-60, >60;
- DESS total score category 1: 0-2, 3-5, 6-10, 11-15, 16-20;
- DESS total score category 2: 0-10, 11-20, 21-30, 31-43.

In addition, the number and percentage of subjects with change in DESS total score from withdrawal baseline by withdrawal visit and during any time point of the withdrawal period (per the worst case value) will be summarized in each of the following categories: ≤ 0 , +1, +2, +3, $\geq +4$.

7.4.7. Columbia Suicide Severity Rating Scale (C-SSRS)

According to FDA draft guidance for suicidal ideation and behavior ([2]), the following C-SSRS outcomes, which have binary responses (yes/no), will be re-ordered and numbered to facilitate the further definitions of the composite endpoint and comparative endpoint of C-SSRS as below.

Category 1 – Wish to be Dead

Category 2 – Non-specific Active Suicidal Thoughts

Category 3 – Active Suicidal Ideation with Any Methods (Not Plan) without Intent to Act

Category 4 – Active Suicidal Ideation with Some Intent to Act, without Specific Plan

Category 5 – Active Suicidal Ideation with Specific Plan and Intent

Category 6 – Preparatory Acts or Behavior

Category 7 – Aborted Attempt

Category 8 – Interrupted Attempt

Category 9 – Actual Attempt

Category 10 – Completed Suicide

Category 11 – Self-injurious behavior without suicidal intent

Unless otherwise specified, C-SSRS table outputs will be presented by analysis group for one analysis time point ‘Any extension (treatment emergent)’, whose definition is given in [Table 10](#).

The analysis time point is applied to suicidal ideation score and ideation intensity total score.

Table 10: Definition of Analysis Timepoint

Analysis Timepoint	eCRF Visit(s) to be Involved	C-SSRS Version /Assessment Period	Derivation Rule
Any extension visit (treatment emergent) ^(a)	all visits in the open-label treatment period (up to EOT)	Since last visit	Most severe value
Any withdrawal visit	all visits after the last study dose	Since last visit	Most severe value

^(a): including all visits in open-label treatment period (see [Section 6.1.1.1](#)).

At each analysis time point, the following binary variables will be derived.

- Any Suicidal Ideation (Categories 1-5)
- Any Suicidal Behavior (Categories 6-10)
- Any Suicidality (Categories 1-10)
- Individual Item for Category 6-11, respectively.

Comparative endpoints for ‘Emergence’ (outcomes that include events that first emerge) and ‘Worsen’ (outcomes that include events that worsen) will be derived as below. See [Table 11](#).

Table 11: Comparative Endpoint of C-SSRS Relative to DB Baseline

Comparative Endpoints	Analysis Time Points Involved	Derivation Rule
Emergence of Suicidal Ideation	DB Baseline ^(a) Any extension visit (treatment emergent) ^(b)	No suicidal ideation at DB Baseline, and any type of suicidal ideation in ‘any extension visit (treatment emergent)’
Emergence of Serious Suicidal Ideation		No suicidal ideation at DB Baseline, and any serious suicidal ideation [ideation score of 4 or 5] in ‘any extension visit (treatment emergent)’
Emergence of Suicidal Behavior		No suicidal behavior at DB Baseline, and any type of suicidal behavior in ‘any extension visit (treatment emergent)’
Emergence of Suicidality		No suicidality at DB Baseline, and any suicidality in ‘any extension visit (treatment emergent)’
Worsening of Suicidal Ideation		Most severe suicidal ideation in ‘any extension visit (treatment emergent)’ is more severe than the most severe value at DB Baseline
^(a) : Definition of DB Baseline: see Table 12 in SEP360-221 SAP and Table 12 in SEP360-321 SAP; ^(b) : see Table 10 .		

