8.2. Subject Exclusion Criteria

A subject who meets any of the following criteria will be excluded in the study.

- 1. Subject is considered by the investigator to be at imminent risk of suicide, injury to self or to others, or damage to property.
- 2. Subject is considered a suicide risk in the investigator's opinion or has any previous history of suicide attempt within the past 12 months.
- 3. Subject answers "yes" to "suicidal ideation" item 4 (active suicidal ideation with some intent to act, without specific plan) or item 5 (active suicidal ideation with specific plan and intent) on the C-SSRS assessment at OL Baseline. Subjects who answer "yes" to this question must be referred to the Investigator for follow up evaluation.
- 4. Subject has a clinically significant abnormality including physical examination, vital signs, ECG, or laboratory tests that the investigator in consultation with the medical monitor considers to be inappropriate to allow participation in the study.
- 5. Subject has a positive urine drug screen (UDS) or breath alcohol test at OL Baseline.

- 6. Subject is breastfeeding.
- 7. Subject is at high risk of non-compliance in the investigator's opinion.

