5.3.1. Columbia – Suicide Severity Rating Scale (C-SSRS)

The C-SSRS is an instrument designed to systematically assess and track suicidal behavior and suicidal ideation throughout the trial. The strength of this suicide classification system is in its ability to comprehensively identify suicidal events while limiting the over-identification of suicidal behavior. The C-SSRS includes the following four sections: Suicidal Ideation, Ideation Intensity, Suicidal Behavior and Actual Suicide Attempts. The C-SSRS is administered by a trained rater at the site.

Severity of suicidal ideation is rated on a 6-point scale from 0='No ideation present' to 5='Active ideation with plan and intent'. A score of 4 or 5 on this scale indicates serious suicidal ideation. Subjects with Type 4 (active suicidal ideation with some intent to act, without specific plan) or Type 5 (active suicidal ideation with specific plan and intent) suicidal ideation during the study will be discontinued from the study and referred to a mental health professional. Suicidal ideation score is defined as the most severe suicidal ideation score (1-5 on the CSSRS) present at the assessment; assign a score of 0 if no ideation is present. The ideation intensity total score is calculated as summation of the five items from the Ideation Intensity scale: frequency, duration, controllability, deterrents, and reasons for ideation. If one or more of these 5 items are missing at a visit, no imputation will be made and the corresponding ideation intensity total score will be set as missing. Items corresponding to frequency and duration are each rated on a scale from 1 to 5 and items corresponding to controllability, deterrents, and reasons for ideation are each rated on a scale from 0 to 5. If the patient did not endorse any suicidal ideation, set the intensity rating to 0. Thus, the possible range for the intensity total score is 0 to 25.

Suicidal behavior is collected as presence/absence of actual attempts, non-suicidal self-injurious behavior, interrupted attempts, aborted attempts, preparatory acts or behavior, and any suicidal behavior. In addition, the number of actual attempts, interrupted attempts, and aborted attempts is captured. Any attempt will be defined as suicidal behavior.

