6.1.1.1. Open-Label Treatment Period (On Treatment)

The day of the 1st dose date in the extension study will be denoted as study Day 1. All measurements at each visit will be assigned a study day relative to this date. All data collected on/after Day 1 for subjects previously randomized to placebo group in core study or on/after the extension baseline visit for subjects previously randomized to dasotraline groups and up to Week 52, including the End-of-treatment/Early Withdrawal visit, will be considered within the open-label treatment phase. That is to say, the start of the open-label treatment period is defined as Day 1 for subjects previously randomized to placebo group and the OL Baseline visit date for subjects previously randomized to dasotraline groups; the end of the open-label treatment phase is defined as the maximum of the last date of administration of study medication and the withdrawal/ completion date.

The start and end of open-label treatment period are given below:

- **Start of treatment period** =
 - = Date of the first study medication administration for subjects previously randomized to placebo group
 - = Date of the OL Baseline visit for subjects previously randomized to dasotraline;
- **End of treatment period** = maximum of the last date of administration of study medication and the withdrawal/ completion date (ie, Week 52/EOT visit date).

Each subject's assessment at each visit in pre-treatment and treatment period will be assigned a study day with respect to the first dose date in the extension study.

- Study Day = Assessment date – the first dose date in the extension study + 1; if assessment date \geq the first dose date in the extension study
- Study Day = Assessment date – the first dose date in the extension study; if assessment date < the first dose date in the extension study

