6.1.3.1. DB Baseline

DB Baseline (ie, Baseline assessment of the double-blind core studies [SEP 360-221, or SEP 360-321]) is defined as the last assessment made on or before the 1st dose of double-blind study medication as described in the SAPs of the core studies.

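### SAP Table 11: the row for emergence of serious suicidal ideation omits subjects who scored 1–3 at DB Baseline, and the comparative endpoints have no OL Baseline version for Pbo-Das

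*SAP*

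**What the plan says.** Frequency and severity of suicidal ideation and behavior on the C-SSRS are part of the primary objective (Protocol 5.1, SAP 2.1). Protocol 15.3.3.2 promises a summary of emergence or worsening by analysis group and names no baseline for it.

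SAP 5.3.1 sets the threshold: "A score of 4 or 5 on this scale indicates serious suicidal ideation". SAP 7.4.7 then defines five comparative endpoints in a table titled "Comparative Endpoint of C-SSRS Relative to DB Baseline". The rule for emergence of serious ideation begins "No suicidal ideation at DB Baseline, and any serious suicidal ideation [ideation score of 4 or 5" and goes on to require that the score occur at any extension visit. The same rules apply to all analysis groups.

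SAP 6.1.3.1 defines DB Baseline in general as "the last assessment made on or before the 1st dose of double-blind study medication". For the C-SSRS the footnote to Table 11 defers: "Definition of DB Baseline: see Table 12 in SEP360-221 SAP and Table 12 in SEP360-321 SAP". Those core-study plans are not part of the documents.

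At entry, exclusion 3 (Protocol 8.2) bars only a positive answer to item 4 or 5, and it applies "on the C-SSRS assessment at OL Baseline".

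SAP 7.4.7.1 also plans three other outputs by analysis group: the incidence of each ideation type and each behavior type at any extension visit, a row for worsening of ideation, and worst-case shifts of the ideation score from both DB Baseline and OL Baseline.

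**The concern.** SAP 7.4.7 describes emergence as covering events that appear for the first time. A subject who scored 2 at DB Baseline and first scores 5 in the extension has newly emerged serious ideation in that sense, yet the row bearing that name excludes the subject. A reader who takes the row at face value sees a smaller count than its label implies, on an outcome within the primary objective.

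The second issue is the reference. Pbo-Das subjects first receive dasotraline in this study, and for treatment-period data the SAP recognizes this: "the start of the open-label treatment period is defined as Day 1 for subjects previously randomized to placebo group". The comparative endpoints nevertheless look back past roughly 12 weeks of placebo to a pre-core value. Change over the placebo phase is thus mixed into a result presented as emergent in the extension.

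**Working it through.** The documents state no event rate or sample-size figure for this endpoint, so there is no planned figure to reproduce. The check applies the Table 11 rules to every possible sequence of scores.

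**Inputs**
- DB Baseline score (DB): 0–5 (scale in SAP 5.3.1; the core entry criteria are not in the documents, so nothing is excluded).
- OL Baseline score (OL): 0–3 (Protocol 8.2, exclusion 3).
- Worst extension score (W): 0–5 (SAP 7.4.7, Table 10).

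**Rules (Table 11)**
- Emergence of ideation: DB = 0 and W ≥ 1.
- Emergence of serious ideation: DB = 0 and W ≥ 4.
- Worsening of ideation: W > DB.

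**Consistency within Table 11.** The rows for emergence of ideation, of behavior and of suicidality each require absence at DB Baseline of the same outcome that they count. The serious-ideation row alone requires absence of a broader outcome. The parallel condition would be no serious ideation, that is DB 0–3.

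**Sequences ending at W = 4 or 5** (logical cases, not patients or probabilities):

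| Sequence | Cases | In serious-emergence row | In worsening row |
|---|---|---|---|
| DB 1–3, any OL | 3 × 4 × 2 = 24 | 0 | 24 |
| DB 0, OL 1–3 | 1 × 3 × 2 = 6 | 6 | 6 |
| DB 1–3, OL 0 | 3 × 1 × 2 = 6 | 0 | 6 |
| Any DB, OL 1–3 | 6 × 3 × 2 = 36 | 6 | not tallied |

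The rows of this table overlap. In all there are 6 × 4 × 2 = 48 sequences, and the present rule counts 1 × 4 × 2 = 8. With DB 0–3 as the condition it would count 4 × 4 × 2 = 32; the other 16 have DB 4–5. With OL 0–3 as the condition it would count all 48, because exclusion 3 already limits OL Baseline to 0–3.

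**Reference for Pbo-Das.** Six sequences have DB = 0, OL ≥ 1 and W between 1 and OL: (OL, W) = (1,1), (2,1), (2,2), (3,1), (3,2), (3,3). All six count as emergence of ideation although nothing rose above the last pre-drug value. In the other direction, take DB = 2, OL = 0, W = 2: ideation resolved on placebo and returned on dasotraline. It is not emergence, because DB is not 0, and not worsening, because 2 is not greater than 2. The same holds for any recurrence at or below the DB Baseline score.

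**Size, on assumptions only.** Let p be the share of enrolled subjects at DB 1–3, k their risk of reaching 4–5 relative to subjects at DB 0, with none at DB 4–5. The share of 4–5 cases outside the row is pk / (pk + 1 − p). For k from 1 to 10:
- p = 2%: 0.02/(0.02 + 0.98) = 2% to 0.20/(0.20 + 0.98) = 17%.
- p = 5%: 0.05/(0.05 + 0.95) = 5% to 0.50/(0.50 + 0.95) = 34%.
- p = 10%: 0.10/(0.10 + 0.90) = 10% to 1.00/(1.00 + 0.90) = 53%.

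Neither p nor k is in the documents.

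**The case against.** The strongest reply is that the information is already in the planned report. SAP 7.4.7.1 tabulates types 4 and 5 with no baseline condition, so every subject who reaches 4 or 5 is counted by group. The shift tables separate a rise from 1–3 to 4–5 from a rise from 1 to 2, and the OL Baseline shift gives Pbo-Das an end-of-placebo reference for the ideation score. Suicide and self-injury events are also an adverse-event category of special interest (SAP 7.4.2). DB Baseline is the stated main reference in both documents, with OL Baseline added where relevant (Protocol 15.3.2, SAP 7.4.1). The study tests no hypothesis (SAP 6.2.2).

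Most of this stands, and it limits the point to derived rows and their reference. It does not remove the point. The type 4 and type 5 rows cannot show emergence because they ignore baseline. The worsening row mixes small and large rises. The shift table leaves the reader to rebuild by hand an endpoint that a labeled row reports differently. For behavior and suicidality, extension incidence is planned, but no shift or emergence output uses OL Baseline.

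A reader might infer more than the documents support:
- That anyone who enrolls with ideation of 1–3 and progresses to 4–5 can never be counted. Exclusion 3 concerns OL Baseline and Table 11 concerns DB Baseline; a subject at DB 0 and OL 1–3 is counted.
- That serious events go unreported. They do not, for the reasons above.
- That the C-SSRS counting window for Pbo-Das opens before first exposure. Table 10 ties it to SAP 6.1.1.1, hence to Day 1; only the comparator is earlier.

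**Conclusion.** The point holds for one derived row and for the reference used by all five comparative endpoints. The serious-emergence row is too narrow for its label: a first rise to 4–5 from a DB Baseline score of 1–3 is outside it in all 24 possible sequences, though all 24 are caught as worsening. The DB Baseline reference can misclassify Pbo-Das subjects in both directions, and emergence of behavior and of suicidality has no last-pre-drug version in any planned output.

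The number of subjects affected cannot be derived. The distribution of DB Baseline scores and the core entry criteria are not given, and the C-SSRS definition of DB Baseline, with its look-back period, sits in the core-study plans. The range of 2% to 53% shows only how the row responds to assumed values; it is not an estimate, and it describes one row rather than cases lost to the report. No decision rule depends on the row, but it belongs to the primary safety objective and is cheap to correct, so it should be corrected.

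**What to change.** In SAP Table 11, define emergence of serious ideation (or add a row so defined) as a score of 0–3 at the reference baseline and 4 or 5 at any extension visit. Name the reference in the rule: DB Baseline, as in the rest of the table. Add a version of the five comparative endpoints against OL Baseline, at least for Pbo-Das, and state in a footnote the look-back period that each baseline covers.

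The cost is SAP wording and a few extra table rows or columns. No new data are needed, since the OL Baseline C-SSRS is carried over from the core-study Week 12 visit (Protocol 11.5.1).

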7.4.7.1. Treatment Period

The number and percentage of subjects with following categories will be summarized by analysis group for any extension visit (treatment emergent).

- each type of suicidal ideation,
- any suicidal ideation,
- each type of suicidal behavior,
- any suicidal behavior,
- any having self-injurious behavior without suicidal intent,
- any suicidality

In addition, for any extension visit (treatment emergent), the number and percentage of subjects with following categories will be also summarized by analysis group.

322

- emergence of suicidal ideation,
- emergence of serious suicidal ideation,
- worsening of suicidal ideation,
- emergence of suicidal behavior,
- emergence of suicidality

Shifts from DB baseline and OL baseline to any post-OL baseline visit (ie, the worst case) in suicidal ideation score will be presented by analysis group, to show the percentage of subjects with values 0 ('No ideation present') to 5 ('Active ideation with plan and intent'). Descriptive statistics (N, mean, standard deviation, median, and range) will be reported for Ideation intensity total score at DB baseline, OL baseline, each post-OL baseline visit, and endpoint for observed value as well as change from DB and OL baseline. Data collected on actual suicide attempts (lethality of actual attempts and potential lethality of attempts) will be presented in a data listing.

All summaries pertaining to the C-SSRS will be based on subjects in the Safety population.

7.4.7.2. Withdrawal Period

The number and percentage of subjects with following categories will be summarized by analysis group for any withdrawal visit for withdrawal population.

- each type of suicidal ideation,
- any suicidal ideation,
- each type of suicidal behavior,
- any suicidal behavior,
- any having self-injurious behavior without suicidal intent,
- any suicidality

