For laboratory tests (hematology, chemistry, urinalysis, lipid panel, hemoglobin A1c), weight, BMI, vital signs, neurological examination, and ECG parameters, descriptive statistics will be provided for observed values and changes from DB baseline and OL baseline for the continuous variables. Frequencies and percentages will be reported for categorical variables by study visit and analysis group. The markedly abnormal values for selected safety parameters will be summarized, as appropriate.

The number and percentage of subjects with suicidal ideation and/or suicidal behavior, emergence or worsening of suicidal ideation or suicidal behavior will be summarized by analysis group for the open-label treatment period, and the withdrawal period, separately.

The CSSA total score, DESS total score, MADRS total score, and HAM-A total score will be summarized by presenting descriptive statistics of observed values and changes from Week 52/EOT by treatment and visit for the withdrawal period.

Analyses for Effectiveness and Subject-reported Health Status: Descriptive statistics of observed values and changes from DB baseline and OL baseline in BE-CGI-S score, EDE-Q modified global and subscale scores (restraint, shape concern, weight concern), EDE-Q modified items 4-6 scores, SDS total score and subscale scores (school/work disability, social life disability, and family life disability), and SF-12 (subjects from Study SEP360-221) two component scores (physical component, mental

² SF-12 collected only for subjects enrolling in this study after completing core Study SEP360-221.

health component) will be summarized by visit and analysis group.

Sample Size: Subjects who complete the double-blind treatment period of the core study, sign the informed consent, and meet all entry criteria will be included in this study. The double-blind core study SEP360-221 plans to randomize approximately 300 subjects and the double-blind core study SEP360-321 plans to randomize approximately 480 subjects. It is estimated that approximately 500 subjects will be eligible for enrollment in this study based on the number of subjects expected to complete treatment in the core studies.

Table 2:Schedule of Assessments

						Treatme	nt Period				
	V1E OL BSN ^a	V2E Week 2	V3E Week 4	V4E Week 8	V5E Week 12	V6E Week 16	V7E Week 20	V8E Week 24	V9E Week 28	V10E Week 32	V11E Week 36
		Dav	Dav	Dav	Dav	Dav	Dav	Dav	Dav	Dav	Dav

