15.3.3.2. Columbia Suicide Severity Rating Scale (C-SSRS)

The number and percentage of subjects with suicidal ideation and/or suicidal behavior, emergence or worsening of suicidal ideation or suicidal behavior will be summarized by analysis group for the open-label treatment period and the withdrawal period, separately.

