3.2. Randomization, Stratification and Blinding

This is an open-label extension study, therefore randomization and blinding is not employed.

322

4. Changes in Planned Analyses

There is not any change made in this SAP from the analyses planned in the protocol.

5. Effectiveness and Safety Variables

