7.4. Safety

7.4.1. Analysis Specifications

All safety analyses and summaries will be based on the safety analysis population.

Unless otherwise specified, safety data will be presented separately by analysis group for the open-label treatment period (for data collected up to the end of open-label treatment period) and withdrawal period (for data collected during the withdrawal period), as appropriate. The CSSA and DESS, which are used to assess physical dependence and withdrawal symptoms, are collected only at the Week 52/EOT and in the withdrawal period; all other safety data are to be

collected in both treatment period and withdrawal period and will be presented by analysis group for the open-label treatment period and withdrawal period, separately, as appropriate.

For continuous data collected in the OL treatment period, actual observed value and change from baseline will be summarized using descriptive statistics (N, mean, standard deviation [SD], median, range, 95% confidence interval [CI] as needed). Where changes are reported, the reference will be to “DB Baseline”. Where relevant, changes from “OL Baseline” will also be reported.

For continuous data collected in the withdrawal period, the actual value, changes from DB and OL baseline (when applicable), and change from withdrawal baseline will be summarized by analysis group at study visits (ie, DB Baseline, OL Baseline, Withdrawal Baseline, and other post-withdrawal baseline visits and withdrawal endpoint).

There will be no imputation of missing values for clinical laboratory test results, vital sign measurements, and ECG evaluations in the by-visit analyses. All analyses of safety data are descriptive. No inferential analyses of safety data are performed.

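### The SAP omits the protocol's withdrawal-period C-SSRS summary of new or worsened suicidality and defines worsening of behavior in neither period, while its Section 4 declares no change

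*SAP*

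**What the plan says.** Protocol 15.3.3.2 plans counts and percentages of subjects with suicidal ideation and/or behavior. In the same sentence it says that "emergence or worsening of suicidal ideation or suicidal behavior will be summarized by analysis group for the open-label treatment period and the withdrawal period". Each period is to have its own summary. The synopsis repeats this: "emergence or worsening of suicidal ideation or suicidal behavior will be summarized by analysis group for the open-label treatment period, and the withdrawal period".

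The SAP treats the two periods differently.

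- **Treatment (7.4.7.1).** Six occurrence categories come first, then a second list introduced by "In addition, for any extension visit (treatment emergent), the number and percentage of subjects with following categories will be also summarized by analysis group". That list has five categories: emergence of ideation, of serious ideation, of behavior and of suicidality, and worsening of ideation.
- **Withdrawal (7.4.7.2).** One list only, introduced by "The number and percentage of subjects with following categories will be summarized by analysis group for any withdrawal visit for withdrawal population". It repeats the six occurrence categories and stops.
- **Definitions (7.4.7).** Table 10 sets up two time points, one for extension visits up to end of treatment and one for all visits after the last dose. Table 11 is titled "Comparative Endpoint of C-SSRS Relative to DB Baseline" and uses only the first. Its worsening rule asks whether the most severe ideation in the extension "is more severe than the most severe value at DB Baseline". It has no worsening rule for behavior.

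SAP Section 4 says: "There is not any change made in this SAP from the analyses planned in the protocol".

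**The concern.** The frequency and severity of suicidal ideation and behavior on the C-SSRS belong to the primary safety objective (Protocol 5.1). The withdrawal period exists to show what happens when the drug is stopped. Protocol 4.3 also names suicidal ideation among the most frequently reported abuse-potential adverse events in adults with ADHD.

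An occurrence count after the last dose mixes two kinds of subject: those whose ideation was present on treatment and continued, and those in whom it began or became worse off drug. The protocol's emergence-or-worsening summary is the one C-SSRS count meant to separate them. A programmer working from the SAP has no derivation for it. A reader of SAP Section 4 is told that nothing was dropped.

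**Working it through.** There is no stated figure to reproduce. The check sets the texts side by side.

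**Step 1: categories listed.**

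| C-SSRS summary | Protocol 15.3.3.2 and synopsis | SAP, treatment (7.4.7.1) | SAP, withdrawal (7.4.7.2) |
|---|---|---|---|
| Occurrence | both periods | 6 categories | 6 categories |
| Emergence or worsening | both periods | 4 emergence + 1 worsening = 5 | 0 |
| of which worsening of behavior | within the wording, both periods | 0 | 0 |

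**Step 2: could the treatment-period endpoints reach into withdrawal?** No. Table 10 ends the extension time point at end of treatment. It also defines a withdrawal time point, but no Table 11 endpoint uses it. The ideation-score shift tables stand under the treatment-period heading.

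**Step 3: does another output supply the count?**

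- SAP 7.4.1 says that for continuous withdrawal data "changes from DB and OL baseline (when applicable), and change from withdrawal baseline will be summarized by analysis group at study visits". This can cover the ideation intensity total. It is a mean change, not a count of subjects who emerged or worsened.
- Discontinuation-emergent adverse events (7.4.2) are event reports, not C-SSRS ratings set against a reference.
- The suicide and self-injury category of special-interest events is summarized for treatment-emergent events. These end 7 days after discontinuation (14 for serious events and deaths), while withdrawal lasts 3 weeks.
- MADRS and CSSA totals and items (7.4.6.2) touch on suicidality, but as scores on other scales.
- By-subject listings show the sequence of ratings but do not summarize it.

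None of these is the count that the protocol names.

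**Step 4: does the reference matter?** The protocol names none for this summary. Take a subject with no ideation at DB Baseline, ideation arising on treatment, and the same ideation at Week 53. Against DB Baseline this subject is emergent in withdrawal. Against Withdrawal Baseline the subject is neither emergent nor worse. Only a reference close to the last dose separates carried-over from new suicidality.

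**Step 5: does Withdrawal Baseline have a weakness?** Yes. For variables other than CSSA and DESS, SAP Table 5.1 lets it fall from Day -5 to Day 3 relative to the last dose. A record on Days 1 to 3 is plausible for early discontinuers, whose end-of-treatment visit follows discontinuation (Protocol Table 2 footnote b; Section 13.2). Because the C-SSRS asks about the time since the last visit, such a record mixes on-drug and off-drug days. Ideation that begins on those days becomes the reference and can never count as emergent.

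**The case against.** The strongest reply is that little is lost. The study is uncontrolled and descriptive, without hypothesis tests. The withdrawal table already shows each type of ideation, so severity is visible. Adverse events, MADRS, CSSA and full listings give further views. This stands as a limit on the consequence. It does not supply the missing count or make Section 4 accurate. The phrase *as appropriate* in SAP 7.4.1 does not help either, since the protocol's C-SSRS sentence has no such qualifier.

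A second reply is that the stated harm depends on a reference the protocol never promised. This is correct. A reader might infer that the SAP departs from a protocol commitment to Withdrawal Baseline for the C-SSRS, but the documents contain no such commitment. The departure is the absent summary. The reference is a proposal.

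A third reply concerns the remedy. Removing the Withdrawal Baseline record from all withdrawal outcomes would hide events on Days 1 to 3 and would contradict Table 10, which takes in every visit after the last dose. This also stands, and the fix is limited accordingly.

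A reader might also count two summaries in two periods and conclude that the SAP delivers three of four in full, so that copying the five treatment rows into withdrawal completes the plan. The documents do not support this: worsening of behavior is undefined even for treatment, and those five rows would leave the protocol's wording unmet in both periods.

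**Conclusion.** The concern holds. The protocol plans an emergence-or-worsening summary for both periods; the SAP lists 5 such categories for treatment and 0 for withdrawal, has no worsening-of-behavior endpoint in either, and declares no change. The gap lies within the primary safety objective and is undeclared.

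The effect on subject counts cannot be estimated, because the documents give no suicidality rate. No test or confidence interval is affected. It would be too strong to say that withdrawal-period suicidality goes unanalyzed: occurrence by type is planned, and other outputs give partial information. The conclusion assumes that the SAP attachments, which are not in the text available for review, do not define these endpoints; the C-SSRS section refers to none of them for that purpose.

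**What to change.** 1. **Table 11 and 7.4.7.2.** For the any-withdrawal-visit time point, add emergence of ideation, serious ideation, behavior and suicidality, and worsening of ideation. State the reference. Withdrawal Baseline is proposed because the other withdrawal-period summaries use it or the protocol's equivalent Week 52 Endpoint (Protocol 15.3.3.3; SAP 7.4.1 and 7.4.6.2). A DB Baseline version may be shown beside it for consistency with Table 11.
2. **Worsening of behavior.** Define it for both periods, for example as a higher category among the SAP's categories 6 to 10 than at the reference, or list its omission in Section 4.
3. **Scope.** Leave Table 10 and the existing occurrence rows unchanged. Exclude the reference record only from the comparison in the new rows. Report separately (a) subjects whose reference record is dated after the last dose, on Days 1 to 3, and shows ideation or behavior, and (b) subjects with no Withdrawal Baseline, which SAP 6.1.3.3 does not impute. Early off-drug events then stay visible.
4. **Section 4.** Correct the no-change statement. If the summary is not added, declare and justify the omission there.

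The cost is SAP wording, five rows in the withdrawal table, two rows for the separately reported subjects, and one row per period if worsening of behavior is defined. The optional DB Baseline version would add its own rows. No new data are needed: the C-SSRS is already collected at end of treatment and at Weeks 53, 54 and 55.
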